5.5 Obstetric History

Obstetric history will be presented in a descriptive manner including mode of delivery, gestational age of delivery, live birth, and abortion.

5.6 Handling of Missing and Uninterpretable Data

5.6.1 Analysis Visit Windows

No analysis visit window will be applied to the analysis. The participants whose blood sample is collected before gestation Week 10 or after gestation Week 18 will also be included in the analysis, but the participants whose blood sample is collected before 8 weeks postpartum need to be excluded from the analysis for postpartum anti-HPA-1a, in order to avoid false negatives.

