Pregnant women at FNAIT risk will be those who are confirmed to be HPA1b/b (HPA-1a negative). This cohort will be enriched for higher FNAIT risk by establishing those HPA-1b/b women who are also HLA-DRB3*01:01 positive. A baseline negative anti-HPA-1a antibody test will establish the absence of detectable antibody and allow assessment of the occurrence of new alloimmunization at Week 10 postpartum (or 10 weeks from the date of the pregnancy-terminating event [ie, abortion (spontaneous/elective) or stillbirth] for pregnancies that do not result in a live birth). Assessment of fetal HPA-1 status will inform on the presence of the antigenic stimulus for maternal alloimmunization (cell-free fetal DNA [cffDNA] HPA-1a positive).

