4.1.3.1 Inclusion Criteria

Pregnant women (≥ 18 years of age) who have provided informed consent for the study.

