4.2.1 Gestation Week 10 to 14 Pre-natal Visit Assessments

- Maternal demographics: year of birth, weight, height, and self-characterized race and ethnicity
- Gestational age in weeks as estimated by the principal investigator
- Obstetric history: mode of delivery, gestational age of delivery, live birth, abortion
- Blood samples will be collected (refer to the study Laboratory Manual for details):
 1. Maternal HPA-1 genotype
 2. Maternal HLA-DRB3*01:01 genotype
 3. Maternal anti-HPA-1a antibodies
 4. Fetal HPA-1 genotype

It is preferred that all samples be collected at the Gestation Week 10 to 14-visit. If all blood samples cannot be collected during one visit, the collection can be split into 2 timepoints. The first timepoint should include blood samples for maternal HPA-1 genotype, maternal HLA-DRB3*01:01 genotype and the maternal anti-HPA-1a antibodies and must be collected at the Gestation Week 10 to 14-visit. The second timepoint should include blood samples for the fetal HPA-1 genotype and should be collected by 18 weeks of gestation.

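### SAP 5.6.1 sets no timing rule for the baseline antibody sample, so a late draw could remove newly immunized women and slightly lower the new-alloimmunization rate

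*SAP*

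**What the plan says.** SAP 5.6.1 opens with "No analysis visit window will be applied to the analysis". It continues: "The participants whose blood sample is collected before gestation Week 10 or after gestation Week 18 will also be included in the analysis". Its one timing exclusion is at the other end of the study: "the participants whose blood sample is collected before 8 weeks postpartum need to be excluded from the analysis for postpartum anti-HPA-1a", with the reason given as "in order to avoid false negatives".

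Protocol 4.2.1 sets two limits, for different samples. The first-timepoint samples are the two maternal genotypes and the anti-HPA-1a antibodies; these "must be collected at the Gestation Week 10 to 14-visit". The later limit concerns the fetal sample: "The second timepoint should include blood samples for the fetal HPA-1 genotype and should be collected by 18 weeks of gestation".

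The inclusion criterion in Protocol 4.1.3.1 has no gestational limit: "Pregnant women (≥ 18 years of age) who have provided informed consent for the study". Neither analysis population in SAP 3.2 has one.

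Protocol section 2 explains why the antibody test is done: "A baseline negative anti-HPA-1a antibody test will establish the absence of detectable antibody and allow assessment of the occurrence of new alloimmunization". Under SAP Table 2 a woman who is antibody positive at baseline is not tested further, and SAP 3.2.2 leaves her out of the Alloimmunization Follow-up Population. SAP 5.3.4 plans no formal sensitivity analysis.

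**The concern.** The four tests do not depend on time in the same way. A woman's HPA-1 and HLA genotypes are the same at any week, so a late sample does no harm there. Her antibody status can change during the pregnancy. The baseline draw is what separates existing from new alloimmunization, and moving it later moves that dividing line.

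Consider a woman who is antibody negative at Weeks 10 to 14, becomes immunized at mid-gestation, and is first tested after that. She is recorded as baseline positive. She disappears from both parts of the rate in SAP 5.3.3.2. She also leaves the higher-risk numerator in SAP 5.3.2 while staying in its denominator. Through this route a late draw can only lower the two figures.

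Both documents plan to use these data as an external control for a future single-arm registration study, so a bias with a fixed direction matters more than in a purely descriptive report. A reader of the planned outputs would also find it hard to see. Estimated gestational age is summarized for the Follow-up Population (SAP 5.3.3.1), but gestational age at antibody sampling is not requested for the women removed as baseline positive.

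**Working it through.** **1. The plan's own figure.** Protocol 4.1.1 and SAP 5.8 expect about 10 to 20 alloimmunized women among 30 to 50 at higher risk.

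- With the 25% to 30% risk stated in Protocol section 2: 30 × 0.25 = 7.5 and 50 × 0.30 = 15. This does not reproduce 10 to 20.
- With the risk derived from the same section's components (10% overall risk, 90% to 98% of cases from the 27% who are HLA-DRB3*01:01 positive): 0.10 × 0.90 / 0.27 = 33.3% and 0.10 × 0.98 / 0.27 = 36.3%. Then 30 × 0.333 = 10.0 and 50 × 0.363 = 18.1, which is close to the stated range.
- The stated counts themselves imply 10/30 = 33% to 20/50 = 40%.

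None of these figures depends on the sampling window. They serve only to set a range for the true risk, taken here as 25% to 40%.

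**2. Formula.** Let p be the true risk of new alloimmunization in women who would be antibody negative at Weeks 10 to 14, f the share of baseline antibody samples drawn late, and q the share of new immunizations that a late draw would already detect. Of N women, N × p × f × q are lost from numerator and denominator alike:

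observed rate = p(1 − fq) / (1 − pfq)

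The documents give neither f nor q. The assumed ranges are f = 5% to 20% and q = 10% to 50%, with late sampling unrelated to risk.

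**3. Results.** Example: p = 30%, f = 20%, q = 50% gives fq = 0.10, and 0.30 × 0.90 / (1 − 0.03) = 0.27 / 0.97 = 27.8%.

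| True risk p | f = 5%, q = 10% | f = 10%, q = 25% | f = 20%, q = 50% |
|---|---|---|---|
| 25% | 24.9% (−0.1 point) | 24.5% (−0.5) | 23.1% (−1.9) |
| 30% | 29.9% (−0.1) | 29.5% (−0.5) | 27.8% (−2.2) |
| 40% | 39.9% (−0.1) | 39.4% (−0.6) | 37.5% (−2.5) |

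Among 40 higher-risk women, cases lost run from 40 × 0.25 × 0.05 × 0.10 = 0.05 to 40 × 0.40 × 0.20 × 0.50 = 1.6. The higher-risk numerator loses the same women, a relative loss of pfq: 0.125% to 4%.

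**4. Scale.** The exact 95% interval for 12/40 (30%) is 16.6% to 46.5%. The largest shift, 2.5 points, is well inside it.

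**5. Samples before Week 10.** The loss in step 2 is zero. An immunization that follows an early draw is still counted as new.

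**The case against.** The strongest reply is that SAP 5.6.1 may be aimed at late fetal genotype samples. Its Week 10 to Week 18 span matches the protocol's combined collection period, and Week 18 appears in the protocol only for the fetal sample, where a late draw does not cause this bias. The study is also open to women presenting at the Week 10 to 14 visit, so late antibody samples may be rare. The study is descriptive, and baseline-positive women are already tabulated, listed and counted in the disposition. All of this limits the size of the problem. It does not supply the missing rule: the sentence names no test, and if it covers only the fetal sample, a late antibody sample falls under the general statement that no window applies.

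A reader might infer more than the documents support:

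- *That early samples also lower the rate.* They do not, as step 5 of the working shows.
- *That Week 18 is the cut-off for the antibody sample.* It is not. Antibody samples drawn between Weeks 14 and 18 are outside the protocol's timing too.
- *That women are in fact being misclassified.* The number of late antibody samples is not given, and women already positive at Weeks 10 to 14 are excluded by design.
- *That the future trial starts from a fixed gestational window, so this cohort would not match it.* Neither document gives an enrolment window for that trial.
- *That the spontaneous-abortion rate is distorted by this rule.* Entry at Weeks 10 to 14, with the fetal sample allowed to Week 18, already leaves little time before the Week 19 boundary. A rule for antibody samples would not change that.
- *That the missing upper limit on the postpartum sample is a comparable fault.* The documents give no basis for the direction or size of any harm from it.

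**Conclusion.** The concern holds as a gap in a stated rule. SAP 5.6.1 lets a late baseline antibody sample count as a valid baseline, although the protocol requires that sample at the Week 10 to 14 visit, and no analysis is planned that would show the consequence. Any bias by this route is downward, for the new-alloimmunization rate and for the higher-risk proportion.

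The likely size is small: about 0.1 to 2.5 percentage points on the new-alloimmunization rate. That range rests on assumed values for the late share (5% to 20%), the share of immunizations newly detectable by the late draw (10% to 50%) and the true risk (25% to 40%). Only the last has support in the documents. If no antibody sample is late, the bias is zero. The case for acting is that the error would be systematic, hard to see in the planned outputs, and cheap to prevent in data meant to serve as an external control.

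**What to change.** In SAP 5.6.1, before database lock:

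- State the timing rule separately for each test, and say to which sample the Week 18 reference applies.
- Keep out-of-window samples for the maternal HPA-1 and HLA genotype frequencies.
- Report the new-alloimmunization rate for women whose baseline antibody sample came from the Week 10 to 14 visit, with later-sampled women in a separate row. Alternatively, keep the all-samples rate and show the restricted rate beside it as a sensitivity analysis. Say where any earlier draws are placed.
- Add gestational age at antibody sampling to the listing of baseline-positive women in SAP 5.3.2.

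The cost is SAP wording, one table row and one listing column. If the restricted rate becomes the main one, a few women move out of it and its interval widens slightly.

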4.2.2 Visit Assessments for Pregnancy Outcomes that are Live Births

For pregnancies that result in a live birth, the assessment of alloimmunization will be at 10 weeks postpartum.

- A blood sample will be collected for the assessment of maternal alloimmunization (refer to the study Laboratory Manual for details), as determined by the presence of detectable anti-HPA-1a antibodies.
- Pregnancy outcome ([Section 3](#)): live births, premature birth, mode of delivery including the date (based on medical records).
- Occurrence of neonatal thrombocytopenia and severe neonatal thrombocytopenia, as determined by a platelet count $< 150 \times 10^9/L$ and $< 50 \times 10^9/L$, respectively, within 72 hours of birth where data are available (based on medical records).
- Interventions used: eg, intravenous immune globulin (IVIG), steroids, fetal platelet transfusions, newborn platelet transfusions.

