Key objectives of Study IPA2002 are to inform on the frequency of higher risk for maternal HPA-1a alloimmunization among pregnant women of different racial and ethnic characteristics presenting for pre-natal care and to assess for the new occurrence of HPA-1a alloimmunization in these women. It is planned that data from this study will provide a contemporary external control for a future single arm registration study of an anti-HPA-1a antibody therapeutic being developed for the prevention of FNAIT caused by maternal alloimmunization to HPA-1a.

Pregnant women at risk for HPA-1a alloimmunization will be those who are confirmed at Gestational Week 10-14 to be HPA1b/b (HPA-1a negative). This cohort of HPA-1b/b women will be enriched for higher risk of alloimmunization by establishing those who are also HLA-DRB3*01:01 positive. A baseline negative anti-HPA-1a antibody test in women who are HPA-1b/b and HLA-DRB3*0101 positive will establish the absence of existing HPA-1a alloantibodies and allow assessment of the occurrence of new alloimmunization at Week 10 postpartum (or 10 weeks from the date of the pregnancy-terminating event [ie, abortion (spontaneous/elective) or

CONFIDENTIAL

stillbirth] for pregnancies that do not result in a live birth). For the women with a baseline negative anti-HPA-1a antibody, assessment of fetal HPA-1 status will inform on the presence of the HPA-1a positive antigenic stimulus for maternal alloimmunization (cell-free fetal DNA [cffDNA]).

This Statistical Analysis Plan (SAP) has been prepared to accompany the clinical protocol for Study IPA2002 version 3.0 (20 May 2022) and the Annotated eCRF version 3 (26 January 2024).

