5.3.3.2 Occurrence of anti-HPA-1a maternal alloimmunization at Week 10 postpartum

The proportion of participants who HPA-1a alloimmunize among the Alloimmunization Follow-up Population will be summarized descriptively.

The proportion will be calculated as (the number of participants with HPA-1a alloimmunization postpartum) / (the total number of pregnant women identified to be at higher risk for HPA-1a alloimmunization, and who have a Week 10 postpartum HPA-1a alloimmunization test result) and with attention to region (Europe vs. North America), first vs. second or later pregnancy, -self-characterized classification of race and ethnicity or by race (White vs. Others), and OMB classification of race and ethnicity.

A comparison table for the summary of OMB classification of Race and Ethnicity between Baseline Screened Population and Alloimmunization Follow-up Population is needed for publication purposes.

A listing of all participants in the Alloimmunization follow up population will be provided, sorted by those with a positive alloimmunization and those with a negative alloimmunization at week 10 postpartum. In addition, a listing with the same data elements will be provided for those participants at higher risk for HPA-1a alloimmunization for whom a 10 week follow up alloimmunization determination is missing.

Data elements for both listings will include Participant ID, Country, maternal age at screening, race (self-characterized), ethnicity, BMI, pregnancy outcome (live births, premature births, stillbirths, spontaneous abortions, elective abortions), reason for termination for pregnancy, gestational age at birth, obstetric history, any interventions for FNAIT during the pregnancy (e.g. IVIG, or interventions other than IVIG), 10-week postpartum HPA-1a alloimmunization status, neonatal platelet count (where available), and additional neonate outcome.

For the separate listing of those who did not have 10 weeks alloimmunization determination, data elements will be the same with the addition of the reason for no determination will be listed as well (e.g. lost to follow-up, withdrew consent) and “unknown” or column deleted for week 10 postpartum HPA-1a alloimmunization status.

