5.3.4 Sensitivity Analyses

No formal sensitivity analysis will be performed.

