5.6.2 Missing Data Imputation

Based on the nature of the study (prospective, non-interventional, natural history), missing data will not be replaced in the statistical analysis of primary and secondary endpoints.

If there is a significant number of missing values for a participant (or if there is confirmed data appearing spurious), a decision will be made following consultation with the sponsor regarding the handling of these data in summaries, prior to DB lock.

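### The planned alloimmunization rate is complete-case only: early-sampled women are dropped whatever their result, untested women are dropped too, and no bound is pre-specified

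*SAP*

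**What the plan says.** - SAP 5.6.1 first says that no visit window applies, then sets one cut-off for the postpartum antibody analysis: "the participants whose blood sample is collected before 8 weeks postpartum need to be excluded from the analysis for postpartum anti-HPA-1a". The reason given is "in order to avoid false negatives". Nothing is said about an early sample that is positive.
- SAP 5.3.3.2 defines the numerator as "the number of participants with HPA-1a alloimmunization postpartum". It limits the denominator to women at higher risk "and who have a Week 10 postpartum HPA-1a alloimmunization test result". SAP 3.2.2 defines the Alloimmunization Follow-up Population in the same way.
- SAP 5.6.2: "missing data will not be replaced in the statistical analysis of primary and secondary endpoints". It leaves unusual cases to a decision with the sponsor before database lock.
- SAP 5.3.4: "No formal sensitivity analysis will be performed".
- SAP 5.3.3.2 plans a separate listing of higher-risk women without a determination, with the reason. Their Week 10 status is shown as unknown or the column is removed, and an early antibody result is not among the data elements. SAP 5.4 counts the women at higher risk and those assessed at 10 weeks.
- Protocol 4.2.2 determines alloimmunization "as determined by the presence of detectable anti-HPA-1a antibodies" in a sample scheduled for 10 weeks. The outcome in Protocol section 3 is also timed at Week 10 postpartum.
- SAP section 1 says that the data "will provide a contemporary external control for a future single arm registration study".

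**The concern.** The 8-week rule is justified by a risk that exists only for negative samples, yet it removes positive ones as well. All women in this cohort were antibody-negative at baseline, so an early positive would be new antibody, and the plan has no place for it. Women with no sample are also removed. What remains is one proportion among the women who were sampled late enough, with nothing to show how far the others could move it.

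That would be a modest gap in a purely internal description. It matters more here because the rate is meant as the comparator for a later single-arm study and rests on few women. Exact confidence intervals are planned, but they describe sampling error among the women analysed and not the effect of who is missing. SAP 5.6.2 leaves room for case-by-case handling and SAP 5.7 plans quarterly analyses, so without a rule set in advance such decisions could be taken after results have been seen.

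**Working it through.** **Notation.** N = higher-risk women; m = women dropped (sampled before 8 weeks, or never sampled); n = N − m; r = positives among the n; e = dropped women with a positive early sample.

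**Inputs from the documents.** N is 30 to 50 and 10 to 20 women are expected to alloimmunize (SAP 5.8). Intervals are exact Clopper-Pearson (SAP 5.2). The documents give neither m nor e, so every value of these below is an assumption.

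**The plan's own figure.** Protocol section 2 gives an overall risk of 10%, with 90% to 98% of cases among the 27% who carry the HLA allele.
- Implied carrier risk: 0.10 × 0.90 / 0.27 = 33.3% to 0.10 × 0.98 / 0.27 = 36.3%.
- Expected cases: 30 × 0.333 = 10.0 to 50 × 0.363 = 18.1, close to the stated 10 to 20.
- The 25% to 30% carrier risk in the same section gives 30 × 0.25 = 7.5 to 50 × 0.30 = 15.0, which is lower.

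**Weight of one woman.** 1/50 = 2.0 points to 1/30 = 3.3 points.

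**Bounds.** The reported rate is r/n.
- *Early positive treated as unknown.* The range over all N is r/N to (r+m)/N. The reported rate always lies inside: r/n ≥ r/N because n ≤ N, and r/n ≤ (r+m)/N because r ≤ n.
- *Early positive counted as alloimmunized.* The range is (r+e)/N to (r+m)/N. The reported rate is below the lower limit when r(n+m) < n(r+e), that is rm < ne, or **e/m > r/n**. It never exceeds the upper limit.

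**Assumed example: N = 40, m = 6, r = 10.**

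| Quantity | Rate | Exact 95% interval |
|---|---|---|
| SAP rate, 10/34 | 29.4% | 15.1% to 47.5% |
| Lower limit, early positives unknown, 10/40 | 25.0% | 12.7% to 41.2% |
| Lower limit, e = 2 counted as cases, 12/40 | 30.0% | 16.6% to 46.5% |
| Upper limit, all dropped women positive, 16/40 | 40.0% | 24.9% to 56.7% |

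With e = 2, e/m = 2/6 = 33.3% exceeds 29.4%, so the reported rate is 0.6 points below the known minimum. With e = 1, the minimum is 11/40 = 27.5% and the reported rate is inside.

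**Other assumed values, early positives counted as cases.**

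| N | m | e | Reported | Range over all N | Reported rate |
|---|---|---|---|---|---|
| 40 | 1 | 1 | 14/39 = 35.9% | 37.5% | below |
| 40 | 4 | 0 | 15/36 = 41.7% | 37.5% to 47.5% | inside |
| 40 | 4 | 1 | 14/36 = 38.9% | 37.5% to 45.0% | inside |
| 40 | 4 | 2 | 13/36 = 36.1% | 37.5% to 42.5% | below |
| 30 | 4 | 2 | 8/26 = 30.8% | 33.3% to 40.0% | below |
| 50 | 4 | 2 | 18/46 = 39.1% | 40.0% to 44.0% | below |

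**Why adding early positives to the main rate is not the answer.** Suppose 6 of 40 women are sampled early, the true rate is 30%, and early samples detect every case. Keeping early positives and dropping early negatives gives (40 × 0.30) / (34 + 6 × 0.30) = 12/35.8 = 33.5%, which is too high.

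**The case against.** The strongest objection concerns the definition. The outcome is antibody detected at Week 10, and a sample before 8 weeks is not that assessment. On this reading an early positive is an unknown, and the reported rate cannot leave the possible range. This stands. A reader might infer that the SAP will report a rate that the data rule out; the documents do not support that, because it needs both an early positive that counts as a case and e/m above r/n.

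A timing rule that ignores the result is also the sound choice for the main rate, as the 33.5% calculation shows. That stands too, and the 8-week rule should stay.

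Next, a reader can derive r/N to (r+m)/N from the planned disposition counts, and the study is descriptive. This is partly right. However, the early results are not in the planned listing, so the other lower limit cannot be derived. A range that each reader has to construct is also weaker than one fixed in advance, and a study without hypothesis tests can still report bounds.

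Finally, the effect is small. The shortfall in the main example is 0.6 points, and the whole 25.0% to 40.0% range lies inside the exact interval of 15.1% to 47.5%. The figures are right, but that interval does not account for selective missingness.

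It is also tempting to argue that mothers of affected infants return more often and so inflate the rate. The documents offer no evidence for this. If such mothers were instead sampled early, they would be dropped and the rate would fall. The direction is unknown.

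**Conclusion.** The concern holds in a limited form. The planned rate is complete-case only, its timing rule discards positives for a reason that applies to negatives, and no analysis shows what the dropped women could do to it. At 2 to 3 points per woman, this matters for a rate meant as an external control.

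Whether the reported rate can fall below a known minimum depends on a rule that the SAP does not state. If an early positive counts, this happens whenever e/m exceeds r/n, and one dropped woman can be enough (35.9% against 37.5%). If it does not count, it cannot happen. Such an error can only be downward, and a control rate that is too low would make a later preventive effect look smaller. It would be wrong to conclude from this that the plan favours the future therapy.

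All values of m and e are assumptions. The change is worth making before the rate is used as a control, but the main analysis is not invalid.

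**What to change.** 1. Keep the SAP 5.3.3.2 proportion and the 8-week rule for the main rate.
2. Replace SAP 5.3.4 with a pre-specified bound over all higher-risk women. Count the dropped women once as all negative and once as all positive, and show both limits with exact 95% intervals beside the main rate.
3. Show the lower limit in two forms: r/N, with early positives treated as unknown, and (r+e)/N, with early positives counted as alloimmunized. Early negatives stay unknown in both. State in the SAP how an early positive is classified.
4. Add the early antibody result and its sample date to the SAP 5.3.3.2 listing of women without a determination, and say that women excluded for early sampling belong in it.
5. In SAP 5.6.1, reconcile the statement that no visit window applies with the 8-week cut-off.

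The cost is some SAP wording, one extra table and two listing fields. The drawback is that the reported uncertainty becomes wider.
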